5.6 Rescue Medications & Supportive Care

5.6.1 Pembrolizumab Supportive Care Guidelines

Subjects should receive appropriate supportive care measures as deemed necessary by the treating investigator. Suggested supportive care measures for the management of adverse events with potential immunologic etiology are outlined below and in greater detail in the ECI guidance document. Where appropriate, these guidelines include the use of oral or intravenous treatment with corticosteroids as well as additional anti-inflammatory agents if symptoms do not improve with administration of corticosteroids. Note that several courses of steroid tapering may be necessary as symptoms may worsen when the steroid dose is decreased. For each disorder, attempts should be made to rule out other causes such as metastatic disease or bacterial or viral infection, which might

require additional supportive care. The treatment guidelines are intended to be applied when the investigator determines the events to be related to pembrolizumab.

Note: if after the evaluation the event is determined not to be related, the investigator is instructed to follow the ECI reporting guidance but does not need to follow the treatment guidance (as outlined in the ECI guidance document). Refer to Section 5.2.1 for dose modification.

It may be necessary to perform conditional procedures such as bronchoscopy, endoscopy, or skin photography as part of evaluation of the event. Suggested conditional procedures, as appropriate, can be found in the ECI guidance document.

- **Pneumonitis:**
 - For **Grade 2 events**, treat with systemic corticosteroids. When symptoms improve to Grade 1 or less, steroid taper should be started and continued over no less than 4 weeks.
 - For **Grade 3-4 events**, immediately treat with intravenous steroids. Administer additional anti-inflammatory measures, as needed.
 - Add prophylactic antibiotics for opportunistic infections in the case of prolonged steroid administration.

- **Diarrhea/Colitis:**

Subjects should be carefully monitored for signs and symptoms of enterocolitis (such as diarrhea, abdominal pain, blood or mucus in stool, with or without fever) and of bowel perforation (such as peritoneal signs and ileus).

 - All subjects who experience diarrhea/colitis should be advised to drink liberal quantities of clear fluids. If sufficient oral fluid intake is not feasible, fluid and electrolytes should be substituted via IV infusion. For Grade 2 or higher diarrhea, consider GI consultation and endoscopy to confirm or rule out colitis.
 - For **Grade 2 diarrhea/colitis** that persists greater than 3 days, administer oral corticosteroids.
 - For **Grade 3 or 4 diarrhea/colitis** treat with intravenous steroids followed by high dose oral steroids.
 - When symptoms improve to Grade 1 or less, steroid taper should be started and continued over no less than 4 weeks.

- **Type 1 diabetes mellitus (if new onset, including diabetic ketoacidosis [DKA]) or ≥ Grade 3 Hyperglycemia, if associated with ketosis (ketonuria) or metabolic acidosis (DKA)**
 - For **T1DM** or **Grade 3-4** Hyperglycemia

- Insulin replacement therapy is recommended for Type I diabetes mellitus and for Grade 3-4 hyperglycemia associated with metabolic acidosis or ketonuria.
 - Evaluate patients with serum glucose and a metabolic panel, urine ketones, glycosylated hemoglobin, and C-peptide.
- **Hypophysitis:**
 - For **Grade 2** events, treat with corticosteroids. When symptoms improve to Grade 1 or less, steroid taper should be started and continued over no less than 4 weeks. Replacement of appropriate hormones may be required as the steroid dose is tapered.
 - For **Grade 3-4** events, treat with an initial dose of IV corticosteroids followed by oral corticosteroids. When symptoms improve to Grade 1 or less, steroid taper should be started and continued over no less than 4 weeks. Replacement of appropriate hormones may be required as the steroid dose is tapered.
- **Hyperthyroidism or Hypothyroidism:**

Thyroid disorders can occur at any time during treatment. Monitor patients for changes in thyroid function (at the start of treatment, periodically during treatment, and as indicated based on clinical evaluation) and for clinical signs and symptoms of thyroid disorders.

 - **Grade 2** hyperthyroidism events (and **Grade 2-4** hypothyroidism):
 - In hyperthyroidism, non-selective beta-blockers (e.g. propranolol) are suggested as initial therapy.
 - In hypothyroidism, thyroid hormone replacement therapy, with levothyroxine or liothyronine, is indicated per standard of care.
 - **Grade 3-4** hyperthyroidism
 - Treat with an initial dose of IV corticosteroid followed by oral corticosteroids. When symptoms improve to Grade 1 or less, steroid taper should be started and continued over no less than 4 weeks. Replacement of appropriate hormones may be required as the steroid dose is tapered.
- **Hepatic:**
 - For **Grade 2** events, monitor liver function tests more frequently until returned to baseline values (consider weekly).
 - Treat with IV or oral corticosteroids
 - For **Grade 3-4** events, treat with intravenous corticosteroids for 24 to 48 hours.

- When symptoms improve to Grade 1 or less, a steroid taper should be started and continued over no less than 4 weeks.
- **Renal Failure or Nephritis:**
 - For **Grade 2** events, treat with corticosteroids.
 - For **Grade 3-4** events, treat with systemic corticosteroids.
 - When symptoms improve to Grade 1 or less, steroid taper should be started and continued over no less than 4 weeks.
- **Management of Infusion Reactions:** Signs and symptoms usually develop during or shortly after drug infusion and generally resolve completely within 24 hours of completion of infusion.

Table 4 below shows treatment guidelines for subjects who experience an infusion reaction associated with administration of pembrolizumab (MK-3475).

Table 4 Infusion Reaction Treatment Guidelines

NCI CTCAE Grade	Treatment	Premedication at subsequent dosing
Grade 1 Mild reaction; infusion interruption not indicated; intervention not indicated	Increase monitoring of vital signs as medically indicated until the subject is deemed medically stable in the opinion of the investigator.	None
Grade 2 Requires infusion interruption but responds promptly to symptomatic treatment (e.g., antihistamines, NSAIDS, narcotics, IV fluids); prophylactic medications indicated for < =24 hrs	Stop infusion and monitor symptoms. Additional appropriate medical therapy may include but is not limited to: IV fluids Antihistamines NSAIDS Acetaminophen Narcotics Increase monitoring of vital signs as medically indicated until the subject is deemed medically stable in the opinion of the investigator. If symptoms resolve within one hour of stopping drug infusion, the infusion may be restarted at 50% of the original infusion rate (e.g.,	Subject may be premedicated 1.5h (\pm 30 minutes) prior to infusion of pembrolizumab (MK-3475) with: Diphenhydramine 50 mg po (or equivalent dose of antihistamine). Acetaminophen 500-1000 mg po (or equivalent dose of antipyretic).

NCI CTCAE Grade	Treatment	Premedication at subsequent dosing
	
from 100 mL/hr to 50 mL/hr). Otherwise dosing will be held until symptoms resolve and the subject should be premedicated for the next scheduled dose.
 
Subjects who develop Grade 2 toxicity despite adequate premedication should be permanently discontinued from further trial treatment administration.
	

Grades 3 or 4 Grade 3: Prolonged (i.e., not rapidly responsive to symptomatic medication and/or brief interruption of infusion); recurrence of symptoms following initial improvement; hospitalization indicated for other clinical sequelae (e.g., renal impairment, pulmonary infiltrates) Grade 4: Life-threatening; pressor or ventilatory support indicated
	
Stop Infusion. Additional appropriate medical therapy may include but is not limited to:
 
 IV fluids Antihistamines NSAIDS Acetaminophen Narcotics Oxygen Pressors Corticosteroids Epinephrine 
Increase monitoring of vital signs as medically indicated until the subject is deemed medically stable in the opinion of the investigator. Hospitalization may be indicated.
 
Subject is permanently discontinued from further trial treatment administration.
	
No subsequent dosing

Appropriate resuscitation equipment should be available in the room and a physician readily available during the period of drug administration.
		

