2.1.1.1 Definition of Dose-Limiting Toxicities

All toxicities will be graded using National Cancer Institute (NCI) CTCAE Version 4.0 (see Appendix).

Dose limiting toxicity (DLT) is defined as the appearance of side effects during treatment that are severe enough to prevent continuation of planned treatment. Dose limiting toxicity is defined as grade 3 or 4 non-hematologic toxicities that is definitely, probably, or possibly related to study drug, excluding alopecia, nausea or vomiting, grade 3 tumor flare, rash, mucositis, radiation dermatitis, need for feeding tube, and grade 3 immune-related events that resolve to grade 1 or less within 28 days. However, Grade ≥ 3 immune-mediated adverse events that include pneumonitis, renal failure nephritis, and elevation of AST, ALT, or bilirubin (with an exception for patients with liver metastases with baseline Grade 2 AST or ALT) should result in discontinuation of pembrolizumab and will be considered DLT (please see Table 3 for details on dose modification) .

In addition, adverse effects that are considered secondary to cisplatin or radiation are not considered DLT (see sections 5.2.1.3 and 5.2.2.7) unless they develop after first dose of pembrolizumab and prior to initiation of cisplatin and radiation. Cisplatin or radiation adverse effects include (but are not limited to):

- Grade 3 or 4 renal impairment (with the exception of renal failure or nephritis determined to be immune-related, which will be considered a DLT).
- Grade 2-4 neurotoxicity including ototoxicity (with the exception of myasthenia gravis and Guillain-Barre syndrome, which will be considered a DLT).
- Grade 3 or 4 mucositis
- Grade 3 or 4 myelosuppression

Although the above should result in dose modifications or delays as stated in section 5.2.1.3, they will NOT be considered DLTs for pembrolizumab on this study, and will NOT interfere with expansion to phase II portion of study.

If a patient is taken off study due to the above and has not yet reached evaluation for toxicity attributed to pembrolizumab, that subject will be replaced with another patient on study.

Non hematologic toxicities that will be attributed to pembrolizumab include:

- Grade 3-4 Pneumonitis
- Grade 3-4 diarrhea/colitis
- Grade 3-4 hyperglycemia
- Grade 3-4 hypophysitis
- Grade 3-4 thyroid dysfunction (hypothyroid or hyperthyroid)
- Grade 3-4 hepatic failure (elevation of AST, ALT, Bilirubin)
- Grade 5 toxicity

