5.2.1.2 Dose Modification for Pembrolizumab

Adverse events (both non-serious and serious) associated with pembrolizumab exposure may represent an immunologic etiology. These adverse events may occur shortly after the first dose or several months after the last dose of treatment. Pembrolizumab must be withheld for drug-related toxicities and severe or life-threatening AEs as per Table 3 below. See Section 5.6.1 and Events of Clinical Interest Guidance Document for supportive care guidelines, including use of corticosteroids.

Table 3
Dose Modification Guidelines for Pembrolizumab-Related Adverse Events

Toxicity	Hold Treatment For Grade	Timing for Restarting Treatment	Discontinue Subject
Diarrhea/Colitis	2-3	Toxicity resolves to Grade 0-1.	Toxicity does not resolve within 6 weeks of last dose or inability to reduce corticosteroid to 10 mg or less of prednisone or equivalent per day within 6 weeks.
	4	Permanently discontinue	Permanently discontinue
AST, ALT, or Increased Bilirubin	2	Toxicity resolves to Grade 0-1	Toxicity does not resolve within 6 weeks of last dose.
	3-4	Permanently discontinue (see exception below) ¹	Permanently discontinue
Type 1 diabetes mellitus (if new onset) or Hyperglycemia	T1DM or 3-4	Hold pembrolizumab for new onset Type 1 diabetes mellitus or Grade 3-4 hyperglycemia associated with evidence of beta cell failure.	Resume pembrolizumab when patients are clinically and metabolically stable.
Hypophysitis	2-3	Toxicity resolves to Grade 0-1	Toxicity does not resolve within 6 weeks of last dose or inability to reduce corticosteroid to 10 mg or less of prednisone or equivalent per day within 6 weeks.
	4	Permanently discontinue	Permanently discontinue
Hyperthyroidism	3	Toxicity resolves to Grade 0-1	Toxicity does not resolve within 6 weeks of last dose or inability to reduce corticosteroid to 10 mg or less of prednisone or equivalent per day within 6 weeks.
	4	Permanently discontinue	Permanently discontinue
Hypothyroidism	2-4	Therapy with pembrolizumab can be continued while treatment for the thyroid disorder is instituted	Therapy with pembrolizumab can be continued while treatment for the thyroid disorder is instituted.

Toxicity	Hold Treatment For Grade	Timing for Restarting Treatment	Discontinue Subject
Infusion Reaction	3-4	Permanently discontinue	Permanently discontinue

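### The DLT exclusion for grade 3 immune-related events that settle within 28 days can exempt an event that ends pembrolizumab under Table 3, and SAP section 8.2 would count that same event

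*Combined protocol and SAP*

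**What the plan says.** - **Section 2.1.1.1, opening.** A DLT is a matter of "side effects during treatment that are severe enough to prevent continuation of planned treatment".
- **Section 2.1.1.1, exclusion.** Among the items removed from the DLT count are "grade 3 immune-related events that resolve to grade 1 or less within 28 days". No condition is set on steroid use or on what later happens to pembrolizumab.
- **Section 2.1.1.1, events restored.** Immune-mediated pneumonitis, renal failure or nephritis, and AST, ALT or bilirubin elevation of grade 3 or worse "should result in discontinuation of pembrolizumab and will be considered DLT".
- **Section 2.1.1.1, attribution list.** A later list of toxicities attributed to pembrolizumab includes "Grade 3-4 diarrhea/colitis", hypophysitis and thyroid dysfunction, with no mention of resolution.
- **Section 5.6.1.** For grade 3 or 4 colitis: "treat with intravenous steroids followed by high dose oral steroids". Then: "When symptoms improve to Grade 1 or less, steroid taper should be started and continued over no less than 4 weeks". Hypophysitis and grade 3-4 hyperthyroidism carry the same taper advice.
- **Section 5.2.1.2, Table 3.** Grade 3 colitis, hypophysitis, hyperthyroidism and other drug-related toxicity are first held. One ground for then discontinuing the subject is "inability to reduce corticosteroid to 10 mg or less of prednisone or equivalent per day within 6 weeks". A note adds permanent discontinuation when a grade 3 drug-related event recurs.
- **Section 2.1.1.** DLTs are assessed from the first dose to the start of the second concurrent cycle. The study proceeds if at most 2 of 6 patients have one.
- **SAP section 8.2.** The same 0-2 of 6 rule is used, but a DLT is any related event of grade 3 or higher, apart from grade 3 tumor flare and toxicities typical of radiation and cisplatin. There is no 28-day exclusion.

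**The concern.** The run-in asks whether pembrolizumab can be given alongside chemoradiation, so an event that ends pembrolizumab is what it most needs to count. Section 2.1.1.1 accepts this: it opens with events that are "severe enough to prevent continuation of planned treatment", and it restores the lung, renal and hepatic events because they stop the drug. It does not restore events that Table 3 holds first and stops later. The SAP counts those events and the 2.1.1.1 exclusion does not.

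With six patients and a cut between 2 and 3, the classification of one patient can decide whether 41 more are enrolled on the concurrent schedule. A choice between definitions made after the events are known would not be a pre-specified decision.

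**Working it through.** The plan gives no operating characteristics for the run-in rule, so there is no figure to reproduce. The check is mainly textual.

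**1. One event under each text.** Take a related grade 3 colitis that reaches grade 1 within 28 days and then leads to discontinuation under Table 3.

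| Text | Score |
|---|---|
| 2.1.1.1, opening sentence | DLT |
| 2.1.1.1, 28-day exclusion | not a DLT |
| 2.1.1.1, attribution list | unclear |
| SAP 8.2 | DLT |

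**2. Can both things happen to one event?** There are two routes.

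*Steroid route.* Assume a linear taper from D mg/day to zero over the minimum 28 days; D is not in the documents. Days to reach 10 mg = 28 × (1 − 10/D). If the six weeks run from the last dose and the drug stays held, grade 1 must be reached by day 42 minus that figure.

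| D (mg/day, assumed) | Days to 10 mg | Latest day of grade 1 after last dose |
|---|---|---|
| 20 | 14.0 | 28.0 |
| 40 | 21.0 | 21.0 |
| 60 | 23.3 | 18.7 |
| 80 | 24.5 | 17.5 |
| 100 | 25.2 | 16.8 |

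Example: onset on day 10 after the first dose and grade 1 on day 25 (15 days later, so inside the 28-day test). A taper from 60 mg reaches 10 mg at 25 + 23.3 = day 48.3, past day 42.

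Table 3 does not say where the steroid clause's six weeks start. Counted from onset, the limit in the example is day 52 and is met. On that count, with D = 60, only events taking about 19 to 28 days to reach grade 1 fall in the gap; with D = 20 none do.

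*Recurrence route.* No taper assumption is needed. Section 5.6.1 warns that symptoms may worsen as steroids are reduced. Two grade 3 episodes, each back to grade 1 within 28 days, each meet the exclusion, while Table 3's note ends the drug.

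**3. Timing against the DLT window.** The window runs from D-21 to D22, about 43 days (about 36 if chemoradiation starts a week early).
- The 28-day test is complete within the window only for onset by about day 43 − 28 = 15 (36 − 28 = 8).
- Six weeks after the second dose (D1) is about D43, some 21 days after the window closes.
- No text says how a pending event is scored.

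**4. Effect on the decision.** Reclassifying one patient matters only if the count including that patient is exactly 3. P(exactly 3 of 6) = 20 p³(1 − p)³, which is 0.185, 0.277 and 0.313 at p = 0.30, 0.40 and 0.50.

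For sensitivity, let p be the DLT rate with these events counted and q the share that the exclusion removes. Both are assumptions. P(proceed) = Σ C(6,k) p′ᵏ(1 − p′)⁶⁻ᵏ for k = 0, 1, 2, with p′ = p(1 − q). For p = 0.40 and q = 0: 0.0467 + 0.1866 + 0.3110 = 0.544.

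| p | q = 0 | q = 10% | q = 25% | q = 50% |
|---|---|---|---|---|
| 0.30 | 0.744 | 0.798 | 0.868 | 0.953 |
| 0.40 | 0.544 | 0.627 | 0.744 | 0.901 |
| 0.50 | 0.344 | 0.442 | 0.596 | 0.831 |

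**The case against.** The strongest reply is that the event is only arguably exempt. The opening sentence of 2.1.1.1 would count it. The attribution list may be meant to identify DLTs: it adds grade 5, which the grade 3-4 definition leaves out, and the text after it sends any additional grade 3-4 toxicity to individual review. SAP 8.2 counts the event outright. This stands, and it is why the point is a conflict between texts and not a settled rule that such events score zero.

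The gap is also narrow. Grade 4 events are not excluded. Lung, renal and hepatic events are already DLTs and, infusion reactions apart, they are the grade 3 events that Table 3 stops at first occurrence. Exempting reversible immune events is a legitimate design choice, and 2.1.1 allows six more patients if toxicity is unclear. All of this limits the size of the point, but none of it says which text governs the count.

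Three stronger readings are tempting, and the documents do not support them.
- *The taper forces discontinuation.* Section 5.6.1 calls its measures suggested, and Table 3 asks for 10 mg or less, not zero. The outcome depends on starting dose, onset and speed of response, none of which is given.
- *The chance of stopping falls from 46% to 10%.* That is p = 0.40 with q = 50%, so 20% of all patients would need to have exactly this event. With q = 10% the fall is from 46% to 37%.
- *A 10 mg steroid test at the evaluation is the remedy.* After the second dose at most about 21 days remain to D22, and a linear taper from 40 mg already takes 21 days. Nearly every steroid-treated grade 3 event after that dose would become a DLT, which cancels the exclusion and adds a clinical threshold.

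**Conclusion.** The point holds as an inconsistency in the run-in decision rule. A grade 3 immune-related event other than pneumonitis, renal or hepatic can meet the 28-day exclusion and still end pembrolizumab under Table 3. SAP 8.2 and the opening sentence of 2.1.1.1 then score the patient as a DLT, and the exclusion does not.

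This follows from the text alone. Only the timing of the steroid route needs assumptions: a linear 28-day taper, a starting dose, and the origin of Table 3's six weeks. The size is one patient's classification, decisive at exactly 3 of 6. How often that would arise cannot be derived from the documents. The sample size of 47 and the primary analysis do not depend on it. It should be corrected before the run-in is evaluated.

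**What to change.** Use one DLT definition for the run-in decision, stated once in 2.1.1.1 and referred to in SAP 8.2, and consistent with Table 3. It should:

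1. Say whether the 28-day exclusion applies at all, since 8.2 now lacks it. If it is kept, add: *the 28-day exclusion does not cover an event that leads to permanent discontinuation of pembrolizumab under Table 3.*
2. Say whether the attribution list in 2.1.1.1 identifies DLTs or only settles causality.
3. State how an event is scored when its resolution or discontinuation status is still pending at the evaluation: for example, hold the decision until the status is known, or count the event as a DLT meanwhile. Give a cut-off for recurrences, which have no time limit.

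Table 3 and section 5.6.1 stay unchanged, and no separate steroid-dose test is added. The amendment needs only a few sentences. Little or no new data is required: section 7.2.4 already asks whether an adverse event caused the product to be discontinued. Steroid dose changes are a weaker source, because 5.5.1 makes recording them optional.

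The costs are a slightly stricter DLT definition and a possible wait. If Table 3's six weeks run from the second dose, the wait is up to about three weeks after D22. For the 28-day test on an event starting just before D22, it is up to about four weeks. If the six weeks run from onset, it is up to about six weeks. Enrollment is already halted for the evaluation, so waiting fits the existing design.

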5.6.2 Cisplatin Supportive Care Guidelines

- **Fluid and Electrolyte Imbalance**

Patients must be vigorously hydrated and diuresed before cisplatin administration as per institutional standard regimens.

- **Nausea and Vomiting**

High dose cisplatin is a highly emetogenic regimen with significant incidence of delayed nausea and vomiting. The following guidelines will be followed:

For acute nausea and vomiting, premedication should include a 5-HT₃ antagonist, such as granisetron 1 mg iv; ondansetron, up to 16 mg iv; or palonosetron, 0.25 mg iv; plus a corticosteroid, such as dexamethasone, up to 20 mg iv.

Breakthrough nausea and vomiting should be managed at the discretion of the medical oncologist or radiation oncologist.

Delayed nausea and vomiting (greater than 24 hours after chemotherapy administration) may be managed by the addition of aprepitant concurrently or with metoclopramide and dexamethasone.

5.7 Diet/Activity/Other Considerations

5.7.1 Diet

Subjects should maintain a normal diet unless modifications are required to manage an AE such as diarrhea, nausea or vomiting.

